Study Center(s)	Multi-center; 10 sites total
Number of Subjects	60
Diagnosis and Main Inclusion Criteria	History of chronic oral food refusal and be primarily fed through a G or G-J tube
Study Product, Dose, Route, Regimen	Megestrol will be dosed at 6 mg/kg/d at weeks 10-11, at 4 mg/kg/d at week 12, at 2 mg/kg/d at week 13, and fully tapered at the end of week 13.
Duration of administration	4 weeks of Megestrol, 24 weeks of iKanEat behavioral intervention
Reference therapy	Placebo for Megestrol
Statistical Methodology	The outcome measure for Aim 1 is a binary variable indicating whether a child obtains 90% or more caloric intake on oral feeding at the end of the intervention. A chi-square test or Fisher's exact test will be used to compare the rates of oral feeding between the two groups.

CONFIDENTIAL

This material is strictly confidential and is intended solely for the guidance of clinical investigation. Do not disclose or use except as authorized in writing by the study sponsor

1 Introduction

This document is a protocol for a human research study. This study is to be conducted according to US and international standards of Good Clinical Practice (FDA Title 21 part 312 and International Conference on Harmonization guidelines), applicable government regulations and Institutional research policies and procedures.

Feeding problems requiring medical intervention occur in 3-10% of children (1). Premature infants are overrepresented among children with feeding problems (2). Improved preterm infant survival has increased the prevalence of feeding problems in older infants and toddlers (3). In addition, severe feeding problems occur in 40-70% of children with chronic medical conditions (4,5). Neonates with long intensive care hospitalizations may lose opportunities for learning to eat and may associate eating with pain or discomfort (6). Gastrostomy (G-) and gastrojejunal (G-J) tube feeding requirements may persist for months or years resulting in chronic oral food refusal. As the prevalence of gastrostomy tube feeding has increased, so have the challenges associated with managing a child with tube feeding and transitioning a child from tube to oral feeding (7,8). Previous research on transitioning children from tube to oral feeding indicates that most programs are inpatient or intensive day treatment, and many children are not successful (8).

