3.2 Primary Study Endpoints

Percent Kilocalories Obtained Orally will be the primary study endpoint. This measure will be obtained using the three day 24 hour food recall. The 24hr food recall is a standardized five-pass method, developed by the US Department of Agriculture for use in national dietary surveillance. Although there are weaknesses to every method of dietary assessment, this one was selected as it is widely used in several large trials and data suggest it is the most valid and reliable method of dietary assessment for children (35) The data will be collected using highly standardized probes by trained research staff, and parents will be presented with paper food models and measuring devices prior to interviews to reference during the recall. Recalls will be analyzed with the Nutritional Data System for Research, version 2016; University of Minnesota, Minneapolis, MN. Although a plethora of information is available from this analysis, the current study will focus on total daily oral calorie intake. This measure will be completed the week following Clinic Visits at weeks 0, 10, 14 and 24.

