4.1 Inclusion Criteria

Subjects must meet all of the following inclusion criteria:

1. Males and females aged 9 months to 9y0m0d at the time of consent.
2. Able to obtain parental or legal guardian written informed consent from subjects as applicable by local laws and regulations.
3. Subjects must have a G or G/J tube.
4. Subjects must receive over 80% of their total daily calorie needs from a tube in order to be classified as tube dependent.
5. Subjects must have a ≥ 3 month history of feeding problems as identified by a diagnosis from a multidisciplinary feeding team, and must have permission from the physician on the team to ensure that they are medically stable enough to participate in a weaning study. (*Please refer to Medically Stable Screening Form to help guide assessment*).
6. Subjects must possess the oral motor skills necessary for eating according to Table 1 in the Appendix.
7. Subjects must possess behavioral skills necessary for mealtime according to Table 2 in the Appendix, or be judged by the professionals on the feeding team as able to meet these behavioral skills by week 10 of the protocol.

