To address Aim 1, analyses will be conducted using Generalized Linear Mixed Models with a logit link within SAS Proc GLIMMIX to model the binary outcome of transitioned to oral feeding (y/n) defined as at least 90 percent of calories consumed orally. Fixed effects (dummy variables) will be entered for each site as described by McNeish and Stapleton (2016) to account for the clustering of the participants within sites. This will result in essentially, a logistic regression model with appropriate standard errors. Sex, age at initiation, treatment condition, and interactions with treatment condition will enable us to examine the effect of group assignment on successful transition to oral feeding by week 24. Interactions between treatment group and sex will be examined but will not be sufficiently powered to reach definitive conclusions about sex differences. In addition to overall effects, subgroup analyses will be reported for males and females to examine treatment effects within sex groups.

To address Aim 2, we will determine whether any of our participants in either group have adrenal sufficiency levels outside of the normal range at any time point. Should any participant have levels outside of the normal range, we will descriptively examine the individual characteristics associated with this, including group assignment, medical diagnoses, sex, and age at initiation. These characteristics will be reported descriptively.

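### The Aim 1 model tests the treatment effect with treatment interactions in it and omits week 0 oral intake, which the trial already collects

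*Combined protocol and SAP*

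**What the plan says.** Section 3.2 of the combined protocol and SAP defines the measured endpoint: "Percent Kilocalories Obtained Orally will be the primary study endpoint". It comes from three days of dietary recall, and on timing the section says "This measure will be completed the week following Clinic Visits at weeks 0, 10, 14 and 24". Section 6.4 holds the first dose of study drug until the week 10 cortisol result is known to be normal, so the week 0 value is pre-drug. (Section 6.1 and Table 3 place the first recall at pre-screening instead; either timing is pre-drug.)

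Section 7.1, Planned Analyses, uses a logit model for Aim 1 "to model the binary outcome of transitioned to oral feeding (y/n) defined as at least 90 percent of calories consumed orally". On terms it says "Fixed effects (dummy variables) will be entered for each site" and then "Sex, age at initiation, treatment condition, and interactions with treatment condition will enable us to examine the effect of group assignment". It adds that the treatment-by-sex interaction will not have enough power for firm conclusions, and that results will also be reported within each sex. Week 0 oral intake is not named. Section 3.3 allows demographics, medical history and outside therapies as covariates, but not baseline intake. The coding of sex, the centring of age, and the contrast that forms the primary test are not stated.

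Eligibility (Section 4.1) limits the baseline range: "Subjects must receive over 80% of their total daily calorie needs from a tube in order to be classified as tube dependent".

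**The concern.** Two things are at stake in how the Aim 1 model is specified.

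First, once a treatment-by-covariate product is in a logistic model, the coefficient labelled treatment is the effect where that covariate equals zero. With sex coded 0/1 it is the effect in one sex, estimated from about half the children. With age uncentred it is the effect at age zero. A plan that does not name the contrast could lose much of its power on a confirmatory question for the sake of an interaction that it already regards as exploratory.

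Second, with 30 children per arm, the arms can differ by chance in starting oral intake. The SD of the difference in baseline means is √(2/30) = 0.258 SD. A gap above 0.25 SD therefore arises in about 33% of randomisations, and one above 0.5 SD in about 5%. The trial collects the measurement needed to adjust for this, but the model does not use it.

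**Working it through.** **Inputs.** From Sections 3.1 and 7.1: 60 children, 30 per arm, 90% success on treatment, detectable odds ratio .18. From the Study Summary: "Multi-center; 10 sites total" (Section 7 names seven). Assumed, because the plan does not say: two-sided .05; interactions of treatment with sex and with age; sexes about equal in number; no true interaction.

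**1. The plan's own figure.** The treatment odds are .9/.1 = 9. The placebo odds are 9 × .18 = 1.62, so the placebo rate is 1.62/2.62 = 61.8%. For the pooled two-proportion test:

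- difference .2817; mean rate .759
- null SE √(2 × .759 × .241/30) = .1104
- alternative SE √((.090 + .236)/30) = .1042
- power Φ((.2817 − 1.96 × .1104)/.1042) = Φ(.626) = .73

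The .80 implied for this case is not reproduced at two-sided .05 (one-sided gives .83). The simulated likelihood-ratio test gives about .77 to .79, and that is the reference below.

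**2. Interactions in the model.** If the treatment coefficient refers to one sex, about 15 children per arm inform it. The same formula with n = 15 gives SEs of .1561 and .1474, and power Φ((.2817 − 1.96 × .1561)/.1474) = Φ(−.165) = .43. The likelihood-ratio test is more liberal in samples this small. Simulation (sex and age in the model, age centred, no site terms) gives:

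| Model | Power | Null rejection |
|---|---|---|
| Interactions, sex 0/1 | about .51 | – |
| Interactions, sex centred | about .78 | .075–.093 |
| Interactions replaced by week 0 intake, log-odds 0 / .5 / 1.0 / 1.5 per SD | .77 / .79 / .82 / .86 | .065–.070 |

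Most of the recovery from .51 therefore comes from taking the interactions out or centring them, not from the baseline term.

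**3. The baseline term alone.** Power without → with week 0 intake:

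| Log-odds per SD (OR) | No site terms | 10 sites, sex, age |
|---|---|---|
| 0 (1.0) | .77 → .76 | .81 → .81 |
| .25 (1.28) | .79 → .79 | .81 → .80 |
| .5 (1.65) | .777 → .780 | .81 → .81 |
| 1.0 (2.72) | .77 → .81 | .80 → .82 |
| 1.5 (4.48) | .78 → .86 | not run |

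**4. What those strengths mean.** Eligibility puts baseline at roughly 0–20% oral. If it is uniform, the SD is 20/√12 = 5.8 points, and the range spans √12 = 3.46 SD. From one end of the range to the other, the odds of success would differ by exp(.5 × 3.46) = 5.6-fold, exp(3.46) = 32-fold, or exp(1.5 × 3.46) = about 180-fold. The first of these brings no visible power gain.

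**5. Model load.** Expected failures are 30 × .10 + 30 × .382 = 3.0 + 11.5 = 14.5. The planned model has 1 intercept + 9 sites + treatment + sex + age + 2 interactions = 15 parameters. The swap gives 15 − 2 + 1 = 14. With site dummies, sex and age but no interactions, null rejection is already about 9–10%. It is about 9–11% once baseline is added.

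**The case against.** The strongest case against is that this is an optional covariate choice. The documents give no association between baseline and outcome. In the prior trial (Section 1.3) completers went from a mean of 31.51% (SD 16.09%) to 100%, so their outcome has no variation from which to estimate one. Eligibility compresses the range. Ten weeks of behavioural work separate the week 0 value from the first dose and may weaken its link to the outcome. All of this stands, and it is why the gain is given as a range that includes zero.

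A reader might infer more than the documents support:

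- *That adjustment gives free precision.* It does not. The analysed outcome is a yes/no at 90%, and every child starts far below that threshold, so this is not the usual case of adjusting a continuous outcome for its own baseline. In a logistic model, adjustment does not shrink the standard error of the log odds ratio. Any benefit appears as power, and the estimand becomes a conditional odds ratio.
- *That the plan calls all its treatment interactions underpowered.* It says so only of sex.
- *That chance imbalance biases the comparison.* Section 5.3 randomises 1:1 within site, so the test remains valid. Imbalance costs efficiency and credibility, not validity.
- *That the planned test has power .51.* That holds only under 0/1 coding with the raw coefficient as the test. A contrast averaged over the sexes is close to the centred case, about .78. The unadjusted chi-square or Fisher test in the Study Summary would not be affected at all.

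None of this shows the swap to be harmful, and it does lower the parameter count.

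**Conclusion.** The point holds as a specification weakness with a cheap remedy. The Aim 1 model combines the confirmatory treatment test with interactions, one of which the plan regards as underpowered. It does not say which contrast is tested, and it leaves out a pre-drug measurement that the trial already collects.

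The larger risk lies in the interactions: power of about .51 against .77 to .78, if sex is coded 0/1 and the treatment coefficient is the test. The baseline term adds about zero up to log-odds .5 per SD, about 2 to 5 points at 1.0 and about 8 to 9 points at 1.5. It costs at most about 1 point if it is not prognostic. A clear gain needs very strong prognosis over a narrow range, so this part is a minor suggestion.

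These figures assume N=60, 90% against 61.8%, two-sided .05 and no true interaction. The comparison with interactions was run without site terms. The 0–20% baseline range is approximate, because eligibility refers to calorie needs and the outcome to calories consumed.

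**What to change.** In Section 7.1, Planned Analyses, before unblinding:

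- Make the primary Aim 1 model main effects only: treatment, site, sex, age at initiation, and week 0 percent of calories taken orally as a continuous covariate. Name the treatment coefficient as the primary test, with its alpha and sidedness.
- Use week 0, not week 10, as the baseline, since the week 10 recall may overlap the first doses. State how a missing week 0 recall is handled.
- Move the sex interaction and the within-sex results to a separate model labelled exploratory. This still meets the commitment to analyse sex as a biological variable. Treat any age interaction the same way.
- Bring the Study Summary's chi-square or Fisher wording into line with whichever test is primary.

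The cost is SAP wording only, with no new data and one parameter fewer (15 to 14). The treatment odds ratio becomes conditional on baseline intake, and the report should say so. The change does not solve the sparsity from the site dummies: about 14.5 expected failures, with null rejection near 9% even without interactions. That needs its own remedy, such as fewer site terms or a penalised or standardised estimator.

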7.1 Sample Size Determination and Statistical Methods

For Aim1 (To assess the efficacy of megestrol as part of the 24 week iKanEat protocol), if at least 90% of the treatment group successfully transitions (in pilot 100% successfully transitioned), with 72 participants, we would have .80 power to detect an odds ratio of .21. With 60 participants, we would have power to detect an odds ratio of .18. If only 75% of the treatment group successfully transitions, we will still have .80 power to detect an odds ratio of .25 with our smallest expected sample size of 60.

For Aim 2 (To assess the safety of megestrol as part of the 24 week iKanEat protocol), all analyses are descriptive, so a power analysis is not conducted.

For Aim 3 (To examine the effect of the transition from tube to oral feeding on parent stress and parent and child quality of life), with 60 participants, we would have .78 power to detect differences in slopes over the four data points equivalent to a standardized effect size of $d=.75$ or larger. With a sample size of 72, there will be .80 power to detect a difference in slopes equivalent to a standardized effect size of .70. To answer those questions in which the grouping factor is success in treatment, such as 3A (The transition to oral feeding will temporarily increase parent stress at week 14 at the cessation of tube feeding, with a return to baseline by week 24) and 3B (The transition to oral feeding will increase parent/child quality of life at 24 weeks compared to week 0), assuming that 60% of the participants across groups are successful, we would have sufficient power to detect effects equivalent to a standardized effect size of $d=.42$ or larger. With a sample size of 60, the minimum detectable effect size would increase to $d=.59$. If 70% percent are successful, with 72 participants we can detect effects equivalent to $d=.61$, and with 60 participants $d=.70$. These are moderate sized effects.

Planned Analyses

CONFIDENTIAL

This material is strictly confidential and is intended solely for the guidance of clinical investigation. Do not disclose or use except as authorized in writing by the study sponsor

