To address Aim 3, we will model parent stress levels, child quality of life, and parent quality of life for participants in both treatment conditions over the four measurement occasions using General Linear Mixed Models. As in Aim 1, fixed effects for site will be added to the model as will sex and age at initiation. Once the shape of the trajectory over time has been modeled, a successful transition to oral feeding indicator, defined as consuming 90% or more of calories orally, will be added to the model at level 2. For 3A, the primary variable of interest will be the time by successful transition interaction on parental stress level. Estimate statements will examine group differences in stress at week 14 and 24. To address hypothesis 3B regarding Quality of Life outcomes, we will initially model the trajectory over time for each outcome with the same set of predictors as in 3A. Of primary interest will be the time by successful transition interaction on subscales for parental quality of life and the parent impact time, general health perceptions, growth and development, and parent impact emotional subscales for child quality of life which showed the greatest response to intervention in our pilot data. It is expected that some subscales such as general health perceptions and parent impact time will show more response to intervention than others. A significant positive slope for some quality of life indicators are hypothesized for those children who transition to oral feeding while stable or declining quality of life ratings are expected for those who are unable to transition to oral feeding. Finally, to complete our analyses of sex as a biological variable (SABV) we will assess study outcomes by gender.

To address Aim 4, the Shannon Index⁶⁰ will be used to determine microbial diversity. Data analysis will be completed using the paired t-test unless the data is not normally distributed in which case analysis will be completed with the Wilcoxon Signed Rank test to compare the index values of patients on each diet.

Heterogeneity of Subjects

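### Aim 1 sex-specific odds ratios may often be non-finite, and within-sex p-values can suggest an absent sex difference; one penalized treatment-by-sex model should be specified

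*Combined protocol and SAP*

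**What the plan says.** All of this is in section 7.1, under Planned Analyses, unless noted.

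- The Aim 1 outcome (at least 90% of calories taken orally, yes or no) is modelled with a logit link. On sites: "Fixed effects (dummy variables) will be entered for each site". The other terms are sex, age at initiation, treatment and interactions with treatment. No penalized or exact method is mentioned.
- The treatment-by-sex interaction will be examined, but the plan says that it "will not be sufficiently powered to reach definitive conclusions about sex differences".
- The next sentence adds a further output: "subgroup analyses will be reported for males and females to examine treatment effects within sex groups". It does not give the model used within each sex, the handling of a non-finite estimate, or the form of the report (interval, p-value or both).
- The Aim 3 paragraph ends on sex as a biological variable: "we will assess study outcomes by gender".
- The Study Summary names a chi-square or Fisher's exact test for the Aim 1 comparison, so a plain 2x2 test within each sex is also a possible reading.

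**The concern.** With about 60 children split by sex and by arm, each cell holds about 15. At 90% success on megestrol, a sex may have no megestrol failure at all, and the maximum-likelihood log odds ratio then runs off to infinity. Site dummies make this more likely, because a site whose children all have the same outcome carries no information on treatment.

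Separately, each sex alone has well under 50% power. If the two within-sex p-values are set side by side, one will often fall below .05 and the other not, even with identical true effects.

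What is at stake is a reported odds ratio with no usable value, or an appearance that megestrol works in one sex only. The overall Aim 1 treatment effect is much less exposed.

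**Working it through.** **Inputs.** The three planning scenarios in section 7.1:
- for 90% success on treatment and N=72: "we would have .80 power to detect an odds ratio of .21";
- at the same success rate but N=60 (.80 implied): an odds ratio of .18;
- with 75% success on treatment, "we will still have .80 power to detect an odds ratio of .25 with our smallest expected sample size of 60".

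Allocation is 1:1 within site (section 5.3). The Study Summary gives 10 sites; Study Locations names 7. Assumed, because not stated: two-sided alpha of .05, a 50/50 sex split, the same odds ratio in both sexes, no true age effect and no site variation.

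**Implied placebo success** = odds × OR / (1 + odds × OR), where odds is the megestrol success odds:
- 9 × .21 = 1.89; 1.89/2.89 = 65.4%
- 9 × .18 = 1.62; 1.62/2.62 = 61.8%
- 3 × .25 = 0.75; 0.75/1.75 = 42.9%

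**The plan's own figure.** No power is stated for the sexes. For the overall .80, in the order above, a pooled two-sided test gives .717, .734 and .727; one-sided it gives .817, .831 and .826. No single variant tried matches all three. That is a separate matter and does not affect this point.

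**No megestrol failure in a sex**, with n = N/4 megestrol children per sex, has probability p^n:
- N=60, 90%: .9^15 = .206; at least one sex, 1 − (1 − .206)² = .37
- N=72, 90%: .9^18 = .150; at least one sex .28
- N=60, 75%: .75^15 = .013; at least one sex .03

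**Adding site dummies and age** (simulation, 800-2,000 trials per setting, separation detected by linear programming). Share of sex-specific treatment odds ratios that are non-finite:

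| Scenario | Refit per sex, 7 sites | Refit per sex, 10 sites | One unpenalized treatment-by-sex model |
|---|---|---|---|
| N=60, 90%, OR .18 | 32% | 39% | 22% (7 sites), 23% (10 sites) |
| N=72, 90%, OR .21 | 22% | 26% | 14% (7 sites) |
| N=60, 75%, OR .25 | 11% | 16% | 2% (7 sites) |

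Refits without age gave 26-37%, 19-25% and 10-15%. A repeat of the single-model check gave 16-24% at 90% success and 2-3% at 75%. Uneven sites with a 60/40 sex split left the refit figures much the same (31-38%, 24%, 12%). The treatment effect from the model without the interaction was non-finite in only 0-6%.

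**Significance in exactly one sex under equal effects** = 2 × power × (1 − power), by exact enumeration of a 2x2 table per sex:

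| Scenario | Fisher power | One sex only | Chi-square power | One sex only |
|---|---|---|---|---|
| N=72, 90% | .299 | .42 | .427 | .49 |
| N=60, 90% | .289 | .41 | .467 | .50 |
| N=60, 75% | .270 | .39 | .432 | .49 |

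For within-sex logit fits, the simulated share was 23-45% by Wald test with equal sites and an even sex split, counting finite fits only (lowest at N=60, 90%, 10 sites), and 48-51% by likelihood ratio. The interaction likelihood-ratio test in the single model was significant in 8-10%. That is above the nominal 5% but far below the one-sex-only figures.

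**The case against.** Three stronger readings are tempting, and the documents do not support them.

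1. *The plan refits the Aim 1 model in boys and in girls.* A reader might infer this, since no other model is offered in section 7.1. It is not stated. The same paragraph describes one model with treatment interactions, and the Aim 3 text uses estimate statements for group contrasts, so sex-specific effects drawn from a single model are an equally open reading. The concern survives, because that model, unpenalized, also leaves 14-24% non-finite at 90% success.
2. *A third of fits fail.* This holds only for N=60, 90% success and a refit with site dummies. Without site dummies the share is about 1-21%.
3. *The sex results will mislead.* No one-sex decision rule is set, no comparison of two p-values is planned, and the sentence just before the subgroup commitment warns about conclusions on sex. A claim of benefit in one sex only would be just such a conclusion, so the warning arguably reaches it. Still, it is attached to the interaction, and the subgroup sentence carries no reporting rule.

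Two further limits stand. Sex appears in no primary hypothesis; section 2 lists it only as a covariate in the exploratory cortisol analysis. And the separation argument does not carry over to Aim 3, whose stress and quality-of-life outcomes use linear mixed models.

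It is also fair to say that a single model alone does not cure separation. Penalization does that work.

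**Conclusion.** The point holds in a limited form. The plan commits to within-sex treatment effects and names only an unpenalized site-dummy logit, which has a material chance of giving no finite odds ratio: about 10-39% of fits if refitted by sex, and about 14-24% (90% success) or 2-3% (75%) from one interaction model. If within-sex p-values are shown, one-sex-only significance arises in about 39-50% of trials by 2x2 tests and 23-51% by model-based tests, with no true sex difference. This can mislead; the documents do not show that it will.

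The figures rest on the assumptions listed with the inputs. Two features of the plan could raise the non-finite share. The pilot success rate was 100% (at 95% success, .95^15 = 46% of sexes would have no megestrol failure). The primary population is protocol-compliant, which may shrink the subgroups. This is a secondary output, but a committed one, and the remedy is cheap.

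**What to change.** Before unblinding, specify the following for Aim 1.

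- Take both sex-specific treatment effects from one Firth-penalized logistic model with site, age, sex, treatment and a treatment-by-sex term. Report each with a 95% profile-likelihood interval.
- As a supplement, give the unadjusted risk difference in each sex with a Newcombe interval, which is defined even with no failures. It omits site and age, so it should not replace the model.
- Base any statement about sex on the interaction estimate and its interval. Give no emphasis to within-sex p-values.
- Extend the existing low-power warning to the subgroup results.

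The cost is a few sentences in section 7.1, minor code changes (possibly a different SAS procedure), slight shrinkage of the estimates, and the loss of within-sex p-values as a headline. Sex-specific reporting is kept. On this ground, nothing need change for the Aim 3 models.
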